## **V. Preservation Techniques**

Following the donor operation wash-out and preservation is performed preferably using UW-CS. In case of kidney donors only, usage of histidine-tryptophane-ketoglutarate (HTK: Custodiol®) in the donor operation and CS preservation is acceptable, but UW is preferred. On the back-table, kidneys will be flushed with 250 ml UW or HTK, respectively. The kidney assigned to MP is then prepared for perfusion using a cannula most suitable for attachment to the perfusion device ("bull-dog patch clamp" or suitable ORS cannulae for the aortic patch). If no aortic patch is present, renal arteries may be cannulated using a straight-end cannula. When perfusion is impossible due to vascular anomaly, preservation methods may be altered and the contralateral kidney is preserved by MP. After cannulation, the assigned kidney will be placed in the prepared perfusion machine, primed with approximately 1000 ml UW-MP. All kidneys assigned to MP will be placed on the device at the donor hospital. The kidney assigned to CS will be preserved in UW-CS or HTK on melting ice.

After adequate packaging, kidneys will be transported to the accepting transplant centers as assigned by ET. Organs will be preserved by either method from donor operation until transplantation.

## **VI. Machine Perfusion**

Prior to the study three Regional Perfusion Centers (RPC) (Groningen, Essen and Leuven) will be established as separate entities that are responsible for the logistics that will allow a safe and high quality procedure using machine preservation according to the state of the art and ruling quality standards. For a good conduct of this study three teams of perfusionists will be trained by professionals from ORS to take care of preservation machines, handle donor kidneys in collaboration with the donor surgeon and accompany the transport of the preservation devices as well as accumulate data for the study. Details concerning the training, responsibilities and standard operation procedures are defined in a separate logistics support protocol (see addendum 4). Each RPC will have a Regional Supervisor who is not the Principle Investigator for that region.

During the study, after reporting a donor for kidney donation, randomization by the ET desk is performed and the transplant coordinator on duty is informed which kidney should be machine perfused and which kidney cold stored. Next the Regional Perfusion Center (RPC) is notified by the transplant coordinator on duty concerning the expected donor operation and told at what point in time a MP-unit ought to be present in the OR at the donor hospital.

At the time the donor operation begins, the RPC will have arranged logistics concerning MP, e.g. the perfusion machine including cannulae, preservation solutions, questionnaires, etc. All details will be available and ready for use in the operating room at the donating center. The RPC, in close collaboration with the responsible transplant coordinator and ET will coordinate and take care of the logistics

concerning transportation of the preservation device. The RPC is responsible for preparing preservation, guiding and instructing surgeons on the spot in the use of common preservation protocol and process. The perfusionist on call is a member of the RPC and is responsible for the individual case. The perfusionist will collect data for the study during the donor procedure, during the first hour of machine preservation and at time of transplantation. Also, he or she will collect data to assess user-friendliness and feasibility of MP. Once kidneys are placed on a MP device they will remain in that preservation mode until delivered to the transplant center OR. The kidney will travel stand-alone from donor hospital to recipient center via the standard transportation method. Perfusate of the MP kidneys will be sampled periodically using the standard machine-ports and aliquots of collected effluent appropriately stored by the perfusionist for quality control and organ viability assessment at a later date. At no time point during preservation any lab results or vascular resistance results may lead to a change of policy or decision to transplant that particular kidney, as the donor kidney pair has been previously accepted for allocation and transplantation on viable grounds according to standard ET regulations.

## **VII. Organ Allocation Logistics**

Organ allocation logistics, including transportation logistics to the assigned transplant center, will be, as usual, the responsibility of ET in close collaboration with the transplant coordinator. In defiance to standard procedures: to prevent possible bias during the study period, ET will at time of offering of the donor kidneys included in the study reveal all pertinent information to the recipient centers but not the preservation method before the individual center has made its appropriate choice for a left or right kidney on recipient or center related grounds. Otherwise, logistics will follow standard policies and the study should not change any procedure or the timing of transplantation in individual recipient centers.

## **VIII. Data Collection**

### Donor, preservation and recipient data

Pertinent data (see addendum 1-3) for the study will be registered in a specially designed web-based database by the perfusionist during the donor, preservation and transplant procedure. Follow-up data (day 0-14, 1, 3 and 12 months) will be filed in the same secure online database by a member of the recipient team in the recipient center. Normal documentation for ET purposes will be carried out in the standard fashion. Recipient centers will be financially compensated for providing follow-up data to be used for the analysis of the study. ET ([name]) in close collaboration with the coordinating principal investigator ([name]) will monitor accrual and quality of data throughout the study. However all PI's share responsibility in encouraging data submission from their transplantation centers.

## **IX. Safety Related Issues**

Organs will be handled according to professional standards within current ET-approved sharing agreements.

The solutions used are the Belzer's Solution for MP (KPS-1) and the University of Wisconsin solution (UW-CS, Viaspan®) for CS. Although UW-CS is preferred, HTK (Custodiol®) is also acceptable for CS preservation.

Adverse effects attributed to the use of either preservation method will be recorded at every donor and recipient operation by the local transplant coordinator, RPC/CTA and transplant recipient center.

Volumes and type of solutions used for in-situ flush will all be documented for each study organ. All solutions and devices used will be CE marked.

If any adjustment to a kidney is required after being placed on a perfusion pump, such adjustment shall only be made while under a biologic hood or in a clean room/operating room environment in order to maintain sterile integrity.

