Nr. of rejection periods (1 - 3 months): \_\_\_\_\_

Complications interfering with graft function not mentioned above: \_\_\_\_\_

Follow up at 1 year post transplantGraft failure:  yes  no

Date of graft failure (dd-mm-yy): \_\_\_-\_\_\_-\_\_\_

Primary cause:

 immunologic preservation

technical - arterial  
 technical - venous  
 infection - bacterial  
 infection - viral  
 other

Graft removal:  yes  no  
Death:  yes  no  
Date of death (dd-mm-yy): \_\_\_-\_\_\_-\_\_\_  
Cause of death:  Tx-related  non-Tx-related  
Serum creatinine at 1 year: \_\_\_\_\_ umol/l  
Creatinine clearance at 1 year: \_\_\_\_\_ ml/min.  
Total nr. of dialysis treatments post-Tx: \_\_\_\_\_  
Currently on dialysis:  yes  no  
    dialysis type:  CAPD  hemodialysis  
Date of last dialysis (dd-mm-yy): \_\_\_-\_\_\_-\_\_\_  
Nr. of rejection periods (3 - 12 months): \_\_\_\_\_  
Complications interfering with graft function not mentioned above: \_\_\_\_\_

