**Transplant coordinator / nephrologist of recipient center**

- ❑ Receives kidney offer without knowing preservation method (preservation method revealed after offer has been accepted)

[NL & NRW: kidney on Lifeport + blood & spleen sent directly from donor hospital to transplant site]

[B: blood & spleen for crossmatching sent directly from donor hospital to transplant site by coordinator donor site; LifePort + extra blood & spleen will be kept at Belgian perfusion lab]

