**Perfusionist 2**

- ❑ Calls OR supervisor in recipient center and informs about scheduled start time of transplant procedure
- ❑ Goes to RPC
- ❑ Takes necessary sampling materials
  - biopsy
    - Acecut Biopsy Gun 16G
    - small and large forceps
    - scalpelblade 15

- pre-tagged 1,5 ml microcentrifuge tubes filled with 200 µl RNALater
  - pre-tagged 1,5 ml microcentrifuge tubes filled with formalin (blue)
- perfusate sampling
  - alcohol swabs
  - syringes 10 ml
  - tagged tubes
- Travels to transplant center before scheduled transplant time
- Upon arrival checks and records MP parameters without revealing these to transplant surgeon
- Collects recipient data
- Scrubs in, disconnects kidney and hands it to transplant surgeon (if requested by surgeon)
- Takes one 10 ml (two if donor > 55 Yr) perfusate samples (viability markers) and one 50 ml sample for chemistry analysis both tagged as ET-number + p3

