**ET desk**

- ❑ Informs recipient hospital about preservation method after kidney has been accepted
- ❑ Arranges transport of kidney in LifePort via the usual route (courier / plane)

[No perfusionist will be present at the recipient site]

[No sampling will be done at recipient site]

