**ET desk**

- ❑ Arranges transport for LifePort back to RPC of origin
- ❑ Requests recipient and transplant data (identical to kidneys stored on ice) from transplant center

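### Section IX records adverse effects only when staff who know the method attribute them to it at an operation, and the follow-up forms have no field for early complications that spare the graft

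*Protocol*

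**What the plan says.** - **The rule.** Protocol section IX: "Adverse effects attributed to the use of either preservation method will be recorded at every donor and recipient operation". The recording is done "by the local transplant coordinator, RPC/CTA and transplant recipient center".
- **Who knows the method.** At randomization, "the transplant coordinator on duty is informed which kidney should be machine perfused and which kidney cold stored" (section VI). For the recipient center, Addendum 4, Scenario 1 has "preservation method revealed after offer has been accepted". The regional perfusion center runs the pump. No blinded assessor is named.
- **Follow-up.** Section VIII has the recipient team file data for days 0-14 and months 1, 3 and 12. Addendum 3 lists the items. Its open field, "Complications interfering with graft function not mentioned above", appears on the 1-month, 3-month and 1-year forms but not on the day 1-14 form.
- **Who collects operation data.** Section VIII gives donor, preservation and transplant data to the perfusionist without limiting this to MP kidneys. In Addendum 4, Scenario 1, the second perfusionist attends the recipient operation of the MP kidney and collects data there. In Scenario 3 (recipient outside the trial region), "No perfusionist will be present at the recipient site", and the Eurotransplant desk "Requests recipient and transplant data (identical to kidneys stored on ice) from transplant center".

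**The concern.** In a randomized comparison, events should be counted whatever their presumed cause, and the comparison itself should then show whether a method is to blame. Section IX reverses this order. A causal judgement by unblinded staff comes before the count, so the count depends on what each observer thinks the method can do. The rule is also tied to two operations, whereas infection, thrombosis and bleeding may appear days later. Section IX itself treats sterility as an issue once a kidney is on the pump.

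At stake is the safety half of the trial's message. The protocol asks whether MP is superior and feasible across an international sharing system. A reader will want to know whether any gain in early function came at the price of complications.

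**Working it through.** The protocol states no figure on harms, so there is nothing to reproduce. The check sets the rule beside the forms.

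**1. What is captured without attribution**

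| Place | Items |
|---|---|
| Addendum 1, each kidney | damage to artery, vein, ureter or parenchyma; washout quality |
| Addendum 2, each recipient | arterial and venous problems; hypotension; free remarks |
| Addendum 3, days 1-14 | graft failure with cause, graft removal, death, hypotension, creatinine, diuresis, rejection, calcineurin inhibitor toxicity, daily dialysis |
| Addendum 3, discharge | discharge date; readmission within 3 months with reason and days |
| Addendum 3, months 1, 3 and 12 | graft failure with cause, graft removal, death, renal function, dialysis, rejection, open complication field |

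These items apply to both arms and do not depend on anyone blaming the method.

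**2. What falls through.** Take a septic episode, or a bleed needing reoperation, on day 5. It is treated before discharge and the graft keeps working.
- Section IX: the event is not at an operation covered by the rule, and it would have to be attributed to the method.
- Day 1-14 form: infection and vascular problems appear only as causes of graft failure, and bleeding does not appear. There is no entry.
- Readmission item: not triggered.
- Open field from 1 month: applies only if graft function was affected.
- What remains is a general remarks line in the immunosuppression block, or a later discharge date with no reason attached.

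Such an event may be noted by chance but is not systematically captured in either arm.

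**3. Who observes.** At the donor operation the same staff see both kidneys. At the recipient operation a perfusionist attends MP kidneys in Scenarios 1 and 2 but not in Scenario 3. The Scenario 3 wording implies that CS data come from the transplant center, whereas section VIII reads as if the perfusionist registers them for all kidneys. Any asymmetry is therefore confined to recipient operations in Scenarios 1 and 2, and the text is not consistent about it.

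**4. Illustration of scale.** The 300 kidneys per arm come from section XIII. The true rates and recording fractions below are assumptions. With true rate t in both arms and recording fractions s₁ and s₂, the recorded rates are p₁ = t·s₁ and p₂ = t·s₂, and the apparent risk ratio is s₁/s₂. This gives 0.9/0.7 = 1.29 or 0.9/0.5 = 1.80. The chance of a significant difference in that direction (two-sided 0.05, independent arms, n = 300) is

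Φ{ [ |p₁ − p₂| − 1.96·√(2·p̄(1 − p̄)/n) ] / √(p₁(1 − p₁)/n + p₂(1 − p₂)/n) }, where p̄ is the mean of p₁ and p₂.

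For t = 5% and 90% vs 70%: p₁ = 0.045, p₂ = 0.035, p̄ = 0.04. Then (0.01 − 1.96 × 0.0160)/0.0160 = −1.34, and Φ = 0.09.

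| True rate | Recorded at 90% vs 70% | Chance | Recorded at 90% vs 50% | Chance |
|---|---|---|---|---|
| 5% | 13.5 vs 10.5 | 9% | 13.5 vs 7.5 | 26% |
| 10% | 27 vs 21 | 15% | 27 vs 15 | 48% |
| 20% | 54 vs 42 | 27% | 54 vs 30 | 81% |

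With equal recording the chance in one direction would be 2.5%. The calculation ignores the pairing. If the fractions are swapped between arms, the false signal points the other way (0.7/0.9 = 0.78; 0.5/0.9 = 0.56).

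**The case against.** The strongest reply is that section IX is one sentence and the protocol collects far more than it suggests. A reader might infer that harms are recorded only at the operations and that postoperative harm is missed, or would appear as zero in both arms. The forms do not support that. Addendum 3 records the major graft and patient outcomes to one year whatever their cause, and readmission reasons would catch part of the rest. Vascular and organ damage at the operations is recorded for every kidney. This part of the reply stands.

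A reader might also infer that the perfusionist's presence inflates the MP count. The documents do not show this either. The presence is limited to recipient operations in Scenarios 1 and 2, and section VIII points the other way on who registers CS data. Section XI has the device supplier managing the Belgian perfusion center, so under-attribution to MP is as conceivable as over-attribution.

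It can also be said that no between-arm test of adverse effects is planned, and that forms and database are still to be developed in Phase I. Both are true and both limit the weight of the point. They do not remove it: the rule as written fixes what is recorded, and no later analysis can recover events that were never entered.

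**Conclusion.** The point holds as a cheap improvement. Two defects remain. The only adverse-effect rule filters events through attribution by unblinded staff at two operations. In addition, no structured field exists for infection, graft-vessel thrombosis, or bleeding or reoperation that spares the graft and is dealt with during the primary stay. The adverse-effect record is thus selective and cannot support a balanced statement on the safety of MP versus CS.

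The direction of any bias cannot be told from the documents. The risk ratios of 1.29 and 1.80 rest wholly on assumed recording fractions. Neither the primary endpoint, nor graft and patient survival at one year, depends on the section IX rule. The conclusion assumes that the forms in Addenda 1-3 are those to be used and that no separate safety document, which is not shown, already closes the gap.

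**What to change.** 1. Reword section IX so that adverse events are recorded for both kidneys of a pair regardless of attribution, at both operations and over the existing day 1-14 and 1, 3 and 12-month windows. Removing the attribution condition alone would leave the timing limit in place.
2. Add yes/no fields to the day 1-14 form for infection or sepsis, graft-vessel thrombosis, and bleeding or reoperation. The recipient center completes them identically in both arms, and they are compared within pairs. Any view on attribution is a separate item that does not decide whether the event is entered.
3. Report MP device failures separately as well, and keep them in the safety results, since they are a harm specific to MP.
4. Reconcile section VIII with Addendum 4 (Scenario 1, second perfusionist; Scenario 3, Eurotransplant desk) on who collects transplant-procedure data for CS kidneys.

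The cost is one reworded rule, three fields on a form that the center already completes and is compensated for, and slightly more data entry. The recorders remain unblinded, so the change reduces selective recording but does not abolish it.

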## **X. Operations**

### Ethics Committee Approval / Local Contacts

The ET Ethics Committee has ruled that no informed consent will be needed for this study. Each PI will seek approval by his center's local Ethics Committee (Groningen, Essen, Leuven).

## **XI. Regional Perfusion Center Operations**

### Equipment, Supplies, Upkeep and Maintenance

At the sole expense of ORS, initial stocking of each participating Perfusion Center shall include:

- 4 LifePort™ kidney transporters
- 20 cassettes
- 20 liters of (KPS-1) machine perfusion solution
- Cannulae, tubing, solutions, gowns, gloves and drapes to supply 20 cases
- Other analytical devices as may be required
- LifePort™ custom transit carts

Thereafter, once inventory of supplies is reduced to 10 cases the Regional Perfusion Center supervisor will submit a formal requisition order to ORS Europe (Brussels) to replenish inventory. Supplies for no less than 5 donor cases shall be maintained in inventory at all times during the study.

Throughout the study, all RPC equipment and supplies will remain the property of ORS.

### Staffing and Coverage

All three RPCs will maintain a 24/7 staff schedule for their respective area. Backing up participant centers in emergency cases shall be determined on a case by case basis.

### Belgium Perfusion Center Management

ORS will manage the Belgium RPC for 24/7 operations.

### The Netherlands and Nordrhein-Westfalen Regional Perfusion Centers

ORS will provide at its sole expense the initial training and set-up for the participating Perfusion Centers in Groningen, The Netherlands, and in Essen, Nordrhein-Westfalen, Germany. Ongoing RPC operating costs will be reimbursed by ORS up to a level sufficient to provide 24/7 coverage of each respective region for the duration of the required perfusions in Phase II of the study.

Upon completion of the study, each participating RPC may acquire from ORS any or all perfusion related facilities, equipment or supplies for fair its then market value.

## **XII. Epidemiology**

DGF is reported to be 25-35% after CS preservation. MP is expected to reduce this rate by 10% (RR 0.9). DGF rates for extended criteria donors and NHB kidney donors are higher, and results will be included in the overall analysis with the possibility of stratification.

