## **II. Trial Design**

A prospective randomized controlled multi center trial of paired kidneys from cadaveric donors (the "study").

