## **III. Objectives/Outline of the Study**

### Main aim of the study:

Does MP with UW-MP (Kidney Preservation Solution: KPS-1) improve early graft function in cadaveric renal transplantation in comparison to UW-CS (Viaspan®)? Assuming the 0-hypothesis that MP and CS give equal early graft function, the alternative hypothesis is that early graft function improves with MP.

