## **XIII. Statistics**

Power analysis is done on the assumption that DGF will be reduced at least by 10% using MP vs. CS. For a power of 0.80 with  $p < 0.05$ , the expected sample size (N) is 300 donors with 300 donor kidneys in either MP or CS, respectively.

Statistical analysis of demographic donor and recipient characteristics will be carried out to check adequate randomization and find relevant differences. To account for the within-donor dependence structure of the data, a multivariate model will be built with a normal gamma frailty term for the donor.

A paired study design leads to a situation in which each donor is the perfect match to himself. On average both treatment arms will have an equal distribution of known and unknown prognostic factors. However, there is no assurance that all prognostic factors are evenly distributed. Therefore, an a posteriori stratification will be performed, implying a modeling of the data using the appropriate multivariate analysis technique. The following preservation and recipient factors are associated with early renal graft dysfunction and thus will be included in the stratification: preservation time (cold ischemic time = CIT), number of HLA mismatches, recent PRA level, recipient age, 1st/retransplant, length of time on dialysis, donor source (e.g. traditional, expanded, non-heart beating) and donor age. Correlation of perfusate organ function testing information to post-transplant graft function and survival will also be done. Lastly, a cost-benefit analysis of the two modalities as regards to graft outcome and survival will be performed.

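### The planned effect of RR 0.9 cannot be reconciled with 300 pairs and power 0.80, which fit an absolute reduction of about 10 percentage points

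*Protocol*

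**What the plan says.** Protocol, section XII (Epidemiology), gives the control rate: "DGF is reported to be 25-35% after CS preservation". The planned effect follows directly: "MP is expected to reduce this rate by 10% (RR 0.9". This is the only place where the 10% is given a scale, and the scale is relative.

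Protocol, section XIII (Statistics), states: "Power analysis is done on the assumption that DGF will be reduced at least by 10% using MP vs. CS". It does not repeat the RR and does not say whether the 10% is relative or absolute. It then claims, "For a power of 0.80" at p < 0.05, that "the expected sample size (N) is 300 donors with 300 donor kidneys in either MP or CS, respectively".

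Two other statements bear on the calculation. Section II describes the design as "A prospective randomized controlled multi center trial of paired kidneys from cadaveric donors". Section III words the hypothesis in one direction: "the alternative hypothesis is that early graft function improves with MP". The control rate used for the power figure, its sidedness and any allowance for pairing are not given.

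**The concern.** A reader who meets RR 0.9 in section XII will carry it into the power statement one section later. Three hundred pairs come nowhere near 80% power for a relative reduction of 10% from a rate of 25-35%. One of the two statements is therefore wrong.

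This matters for the primary endpoint because the reading of a non-significant result depends on which effect the trial could have detected. If about 10 percentage points was meant, the printed RR invites readers to believe that 300 pairs can exclude a benefit roughly a third as large. If RR 0.9 was meant, the trial has little chance of showing it.

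**Working it through.** **Inputs.** Control DGF rate p1 = 25-35% (section XII; 30% is the midpoint, used as an assumption). Effect RR 0.9 (section XII) or a reduction of 10% on an unstated scale (section XIII). Alpha 0.05, power 0.80 and n = 300 pairs (section XIII). Assumptions: two-sided testing first, one-sided as a variant; within-donor correlation phi from 0 to 0.5, because the protocol gives none.

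**Formulas.** Let d = p1 - p2, pbar = (p1 + p2)/2, z_a = 1.960 (two-sided) or 1.645 (one-sided), z_b = 0.842.

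- Unpaired: n per arm = [z_a·sqrt(2·pbar(1 - pbar)) + z_b·sqrt(p1(1 - p1) + p2(1 - p2))]² / d². Power = Φ{[d·sqrt(n) - z_a·sqrt(2·pbar(1 - pbar))] / sqrt(p1(1 - p1) + p2(1 - p2))}.
- Paired (McNemar, normal approximation): p11 = p1·p2 + phi·sqrt(p1(1 - p1)p2(1 - p2)) and discordant share D = p1 + p2 - 2·p11. Pairs = [z_a·sqrt(D) + z_b·sqrt(D - d²)]² / d². Power = Φ{[d·sqrt(n) - z_a·sqrt(D)] / sqrt(D - d²)}.

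**Step 1: reproduce the plan's figure.** Take 10% as absolute, 30% to 20%, two-sided and unpaired:

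- n = (1.960 × 0.6124 + 0.842 × 0.6083)² / 0.10² = 293.2, so 294 per arm.
- Power at 300 = Φ[(0.10 × 17.32 - 1.960 × 0.6124) / 0.6083] = Φ(0.874) = 0.81.
- McNemar with phi = 0 gives 296 pairs and power 0.81.

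The ends of the stated range, two-sided and unpaired, give:

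- 25% to 15%: 250 per arm, power 0.87 at 300.
- 35% to 25%: 329 per arm, power 0.76 at 300. With phi = 0.1 this case needs 299 pairs.

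An absolute reduction of about 10 points therefore reproduces the stated 300 and 0.80.

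**Step 2: put in RR 0.9.** For 30% to 27%, two-sided and unpaired:

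- Power at 300 = Φ[(0.03 × 17.32 - 1.960 × 0.6384) / 0.6380] = Φ(-1.147) = 0.13.
- n for 80% power = (1.960 × 0.6384 + 0.842 × 0.6380)² / 0.03² = 3,553.1, so 3,554 per arm.

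The full range with 300 pairs:

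| DGF, CS to MP | Two-sided, phi 0 | One-sided, phi 0 | Two-sided, phi 0.5 | One-sided, phi 0.5 | n per arm for 80% power (two-sided, phi 0) |
|---|---|---|---|---|---|
| 25% to 22.5% | 0.11 | 0.18 | 0.17 | 0.26 | 4,548 |
| 30% to 27% | 0.13 | 0.20 | 0.21 | 0.31 | 3,554 |
| 35% to 31.5% | 0.15 | 0.23 | 0.25 | 0.36 | 2,843 |

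The last column is from the unpaired formula; McNemar with phi = 0 differs by at most 3 pairs. At phi = 0.5, two-sided, the requirement is still 2,280, 1,782 and 1,427 pairs.

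**Step 3: compare the effects.** A fall from 30% to 20% is RR 0.20/0.30 = 0.67. RR 0.9 from 30% is a fall of 3 points. The two readings of 10% differ by a factor of about three in absolute terms.

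**The case against.** The strongest reply is that section XIII, the only section describing the power analysis, never mentions RR 0.9, and that its figures reproduce if 10% means percentage points. On that view the calculation is sound and only a parenthesis in section XII is wrong. This stands in large part, and it rules out some stronger readings.

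- **That the stated power is wrong by some 65 points.** The gap of 65-69 points (0.80 less 0.11-0.15) exists only if RR 0.9 was the effect used for planning, tested two-sided with no within-donor correlation. The documents do not show that it was. What they show is a contradiction.
- **That the trial would miss a true benefit 85-90% of the time.** This carries the same conditions. One-sided testing, which the directional hypothesis in section III might suggest, gives power 0.18-0.23 without correlation. Pairing at phi = 0.5 gives 0.17-0.25 two-sided.
- **That 300 can come only from 30% to 20%, unpaired and two-sided.** It cannot be pinned down so tightly, since 35% to 25% with phi = 0.1 needs 299 pairs.
- **That the unstated test and sidedness are a separate fault.** A statistical analysis plan may supply them, so they are not counted as one here.

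What the reply does not remove is the mismatch. Section XII prints an effect size, section XIII prints a power and a sample size, and no variant tried brings them together. An analysis plan cannot settle which of two conflicting figures in the protocol was intended.

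**Conclusion.** The concern holds as a contradiction between sections XII and XIII on the design assumption for the primary endpoint. RR 0.9 on a control rate of 25-35% cannot coexist with 300 pairs and power 0.80. For that effect the power is about 0.11-0.15 two-sided without within-donor correlation, and no higher than 0.36 under the most favourable combination checked (one-sided, phi = 0.5, control rate 35%).

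Because 300 and 0.80 fit an absolute reduction of about 10 points, the RR label is the likelier error. That is an inference from the arithmetic, and only the sponsor can confirm it. The one-sided variants and the correlation values are assumptions, since the protocol gives neither sidedness nor correlation.

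**What to change.** The sponsor should confirm which effect was meant and make sections XII and XIII say the same thing.

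- **If absolute:** in section XII, replace the RR of 0.9 with an absolute reduction of 10 percentage points, e.g. 30% to 20% (RR 0.67), and use the same words in section XIII. Keep 300 pairs and power of about 0.80. Add that power for RR 0.9 is only about 0.11-0.15 (two-sided, ignoring pairing), so a non-significant result would not exclude an effect of that size.
- **If RR 0.9:** in section XIII, replace the power of 0.80 for 300 pairs with about 0.11-0.15 (two-sided, ignoring pairing).

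In both cases, give the control rate, the sidedness and the assumed within-donor correlation next to the power figure.

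The cost is wording in two sections. Neither version adds donors, but the stated detectable effect or the stated power becomes less favourable than it now reads.
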